## 4 STUDY DESIGN

### 4.1 OVERALL DESIGN

After receiving approval for the study, we will conduct a prospective single institution randomized clinical trial assessing if using a TAP block perioperatively can reduce pain scores after surgery. Other endpoints include whether there are differences in pain medication usage and complications.

Patients will be screened by research team members and attending surgeons. If the patient is interested, we will consent them for the study after they understand the study details, procedures, and expectations. We will then consent using IRB approved study consent forms and procedures. Patients will undergo a laparoscopic inguinal hernia repair according to standard procedures. Our study will assess if a TAP block impacts pain scores. Patients will be randomized to receive the intervention or placebo. Sequentially numbered sealed opaque envelopes with group allocation inside will alert the anesthesiologist/ surgeon to order Tap block composed of 0.25% bupivacaine or placebo (normal saline).

Inguinal hernia repair will be performed in standard fashion that each individual surgeon is familiar with. No additional tests or blood work outside the standard of care for IHR will be performed for research purposes. In addition, some patients will be given TAP blocks before surgery to help in pain management. In addition, patients will be discharged with a worksheet on which they are to record analgesic use and pain scores on postoperative days one, two, three and four. They are expected to bring the completed log to their two-week follow up visit with their surgeon. Patients may also expect to receive a phone call from a member of the surgical team to remind them to record these metrics.

The TAP block is done pre-procedure using 0.25% bupivacaine. If patients weigh<100 kg, they will receive a total of 50 mL (25 mL on each side of the abdominal wall). If patients weigh>100 kg, they will receive a total of 60 mL (30mL on each side of the abdominal wall). The TAP plane is identified using ultrasound. All anesthesiologists (not surgeons) working with the attendings involved in this study have been trained in this technique; it is a routine part of their practice. It is anesthesiologists who will be performing the block.

Patients will be discharged with a worksheet /survey on which they are to record analgesic use and pain scores on postoperative days one, two, three and four. They are expected to bring the completed log to their two-week follow up visit.

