## 1 PROTOCOL SUMMARY

### 1.1 SYNOPSIS

Title:	Transabdominal plane (TAP) Blocks for Laparoscopic Inguinal Hernia Repair
Grant Number:	
Study Description:	Inguinal hernias are bulges in the groin region that arise from weaknesses in the abdominal wall. Often, due to discomfort, pain or cosmetic dissatisfaction, these hernias must be surgically repaired. The use of a transabdominal plane (TAP) block—a local injection given in the abdomen to block pain receptors on nerves—during surgery can presumably decrease postoperative pain. The aim of our study is to investigate whether the use of a TAP block can decrease the use of opioids and pain scores after surgery.
Objectives*:	The aim of our study is to examine outcomes and pain control after surgery in patients who underwent laparoscopic inguinal hernia repair (IHR) with the use of perioperative transabdominal plane (TAP) block. Research Question: Does transabdominal plane block improve pain when undergoing inguinal hernia repair?
Endpoints*:	To evaluate whether preoperative TAP blocks improve pain score (primary end point) and decrease opioid use (secondary endpoint) after an inguinal hernia repair. Other end points- complications after surgery.
Study Population:	We will be enrolling 100 patients from Mount Sinai Hospital undergoing laparoscopic inguinal hernia repair.
Phase* or Stage:	
Description of Sites/Facilities Enrolling Participants:	All enrollment will occur at one site (Mount Sinai Hospital) at Faculty Practice Associates and Emergency Department.
Description of Study Intervention/Experimental Manipulation:	The study intervention is the administration of a TAP Block (0.25% bupivacaine or placebo (Saline). For patients weighing <100 kg, they will receive a total of 50 mL (25 mL on each side of the abdominal wall). If patients weigh >100 kg, they will receive a total of 60 mL (30mL on each side of the abdominal wall). The TAP plane is identified using ultrasound. All anesthesiologists working with the surgical attendings involved in this study have been trained in this technique; it is a routine part of their practice. Anesthesiologists will be performing the block.
Study Duration*:	2 Years
Participant Duration:	2 Weeks

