#### 5.5 STRATEGIES FOR RECRUITMENT AND RETENTION

100 patients will be recruited at Mount Sinai Hospital who are scheduled to receive a laparoscopic inguinal hernia repair. Patients will be screened by research team members and attending physicians. Recruitment will occur if a patient is interested in the study and they meet the inclusion criteria and do not meet exclusion criteria. Potential patients will receive an explanation of study procedures and expectations. If they would like to participate, they will be consented according to standard procedures. Patients will be discharged with a worksheet that asks for pain levels and pain medication usage after their operation. They will be expected to bring the completed sheet during their post-operation follow up visit. There will be no incentives for participation in the study.

Given that patients will be enrolled in the clinic and the emergency department after presenting with a disease, they may be overwhelmed and may have limited time to process the risks and benefits of enrolling in this trial. To address the increased vulnerability as described above, we will train all persons involved in the consent process in best practices for consenting a patient. Ultimately, the physician will make the decision for enrollment.

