## 8 STUDY ASSESSMENTS AND PROCEDURES.

### 8.1 ENDPOINT AND OTHER NON-SAFETY ASSESSMENTS

Study recruitment will include patients who are schedule for a laparoscopic inguinal hernia repair and meet the inclusion criteria but not the exclusion criteria. The screening will be completed by the research team and/or physician. If a patient is interested, they will be approached to consent for the study. If they are still interested and understand the study and its expectations, they will consent using standard consenting procedures. The intervention will be given perioperatively and the procedure will continue according to standard procedures. No deviation from standard care will be made for the inguinal hernia repair. The patient will be discharged with worksheet asking for pain scores and pain medication usage.

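### The pain and analgesic worksheet is issued at discharge, and no readable section says how days 1 to 4 are recorded for a patient still in hospital

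*Combined protocol and SAP*

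**What the plan says.** **When the form is issued.** Section 4.1 states that "patients will be discharged with a worksheet on which they are to record analgesic use and pain scores on postoperative days one, two, three and" (through day 4), and its closing paragraph repeats this: "Patients will be discharged with a worksheet /survey on which they are to record analgesic use and pain scores". Section 5.5 has "Patients will be discharged with a worksheet that asks for pain levels and pain medication usage after their operation", and section 8.1 has "The patient will be discharged with worksheet asking for pain scores and pain medication usage".

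**How it comes back.** Section 4.1: "They are expected to bring the completed log to their two-week follow up visit with their surgeon". The same section mentions that a reminder call may be made. It does not describe the call as a way of collecting scores.

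**Who is enrolled.** Section 5.1 admits any patient having a laparoscopic inguinal hernia repair at the hospital, and nothing in 5.1 or 5.2 requires same-day discharge. The synopsis says "All enrollment will occur at one site (Mount Sinai Hospital) at Faculty Practice Associates and Emergency Department", and section 5.5 says "patients will be enrolled in the clinic and the emergency department after presenting with a disease". Sections 5.5 and 8.1 also describe the patients as scheduled for repair.

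**What the data feed.** Section 3 makes the change in pain score primary and pain medication secondary. Section 9.4.2 names a rank-sum test for the primary endpoint. Neither section names a day. Section 4.4 treats a partly filled worksheet as completion, and section 9 gives no method for missing data.

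**The concern.** The collection rule works as written only if every patient is home before postoperative day 1, and the protocol does not make that a condition. For a patient discharged on day 2, say, the form arrives after the day-1 entry was due and perhaps after the day-2 entry as well. No readable section tells staff to record pain or analgesics for the study meanwhile. Those entries would be blank or reconstructed from memory, and drugs given on the ward might not reach the worksheet.

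The discharge date is settled after randomization and may depend on pain, which the block is expected to lower. If more saline patients stay in because of pain, the highest early scores and heaviest early analgesic use would be missing or recalled more often in the saline arm. That would understate any benefit on the recorded days closest to the injection.

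**Working it through.** **1. The plan's own figure.** Section 9.2 gives a total of 100 at 1:1, so 50 per arm. It states no effect size, SD, power or dropout, so the figure cannot be reproduced. What 50 per arm can detect at two-sided 0.05 and 80% power is:

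- (1.960 + 0.842) × √(2/50) = 0.56 SD.
- Allowing for the rank test's efficiency of 3/π against normal data: 0.560 / √0.955 = 0.57 SD.

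**2. Plain loss of day-1 scores.** The loss rates are assumptions, taken as equal in both arms. The middle column is 2.802 × √(2/n). The power column uses the normal approximation and assumes a true effect of 0.5 SD.

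| Day-1 loss | n per arm | Detectable difference (SD) | Power at 0.5 SD |
|---|---|---|---|
| 0% | 50 | 0.56 | 70.5% |
| 2% | 49 | 0.57 | 69.7% |
| 5% | 47.5 | 0.58 | 68.3% |
| 10% | 45 | 0.59 | 66.0% |
| 20% | 40 | 0.63 | 60.9% |

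**3. Loss related to pain.** Let f be the share of an arm with no day-1 score and g the amount by which those patients would exceed the rest of their arm. The full arm mean is M = (1 − f)·m + f·(m + g), so the observed mean is m = M − f·g. The shrinkage of the block benefit is then

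(f × g in the saline arm) − (f × g in the block arm).

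If f and g are the same in both arms, this is zero. With g equal in the two arms at 0.5 to 1.0 SD, and a true effect of 0.5 SD:

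| Missing, block vs saline | Shrinkage (SD) | Power |
|---|---|---|
| 2% vs 6% | 0.02 to 0.04 | 65.2% to 61.5% |
| 5% vs 15% | 0.05 to 0.10 | 56.9% to 47.5% |
| 10% vs 20% | 0.05 to 0.10 | 54.6% to 45.4% |

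The power figures include the reduced sample as well as the shrinkage. For 5% vs 15%, the average loss of 10% alone already lowers power from 70.5% to 66.0%.

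**4. The same in score points.** Assume 5% to 10% of block patients (2.5 to 5 of 50) and 10% to 20% of saline patients (5 to 10 of 50) are affected, with an excess of 2 points.

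- Saline mean too low by 0.10 × 2 to 0.20 × 2 = 0.2 to 0.4.
- Block mean too low by 0.05 × 2 to 0.10 × 2 = 0.1 to 0.2.
- Net, over all combinations: smallest 0.2 − 0.2 = 0, largest 0.4 − 0.1 = 0.3 points.

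**5. Limits of the check.** Every rate and excess in steps 2 to 4 is assumed, as is the 0.5 SD effect. The protocol names no pain scale, so 2 points has no fixed meaning. The formula concerns means and treats every affected entry as blank. The planned test uses ranks, and some entries would be recalled instead. The figures show how the mechanism works and do not estimate what this trial would lose.

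**The case against.** The strongest reply is that a take-home sheet starting on day 1 suggests patients are expected to be home by then. If all are, nothing is lost by this route. That stands, and it is why the point must be conditional. Several stronger readings should be resisted:

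- **That early scores are in fact being lost selectively.** The documents give no length of stay and do not say that anyone remains in hospital on day 1. A late-discharged patient can also fill in earlier days from memory, so recall error is as likely as loss.
- **That emergency department enrolment means admitted or urgent cases.** It says where patients are enrolled. Sections 5.5 and 8.1 describe scheduled repairs.
- **That the primary time point is damaged.** Sections 3 and 9.4.2 name no day, so day 1 is one of four recorded days. Section 2.2 also plans mixed models over time, which can use partial records, although 9.4.2 names only the rank test for the primary endpoint.
- **That inpatient analgesics will certainly go uncounted.** Section 6.5 asks participants to record pain medication with no limit to home use, and section 10.1.3 keeps a link to the medical record.

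Other provisions do not close the gap. Section 10.1.9.1 promises hard-copy worksheets for enrolled participants, and 10.1.3 allows further parameters to be retrieved later. Both are generic, and neither says that pain or analgesics are recorded for the study during a stay. Section 8.2 tracks complications and events, not pain scores. Section 1.3, where such assessments might be listed, has no readable content in the text available, and nothing is inferred from that.

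**Conclusion.** The point holds in conditional form. Every section that says when the worksheet is issued ties it to discharge, no readable section covers hospital days, and eligibility does not rule them out. If any patient is still in hospital on day 1 or later, the entries for those days would be missing or recalled, possibly in relation to pain.

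Bias in the comparison further requires that the share affected, or the excess pain of those affected, differ between arms. The plausible direction is toward no effect, since the block is expected to reduce pain and so perhaps delayed discharge. The size cannot be derived from the documents and may be zero; the illustrative 0 to 0.3 points and 0.02 to 0.10 SD rest wholly on assumed rates. This is a cheap improvement worth making before enrolment, because a score not taken at the time cannot be recovered later.

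**What to change.** Amend sections 4.1, 5.5 and 8.1 so that:

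- every randomized patient receives the worksheet before surgery;
- postoperative days are counted from surgery for everyone, whatever the discharge date;
- for any day spent in hospital, the same items are completed at the bedside or taken from the nursing pain score and the medication record.

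For the last item to work, the protocol should name the pain scale, so that bedside, chart and home entries are comparable. Recording the discharge date would let the analysis report, by arm, how many patients were in hospital on each day.

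The cost is an earlier handover of the same form and a small amount of chart extraction for any inpatients. Nothing about the block, the surgery or discharge decisions changes.

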#### 4.4 END-OF-STUDY DEFINITION

End-of-study is defined as completing the intervention and any portion of worksheet. Study times are expected to take place during a 2 week time period.

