### 9.2 SAMPLE SIZE DETERMINATION

Based on previous clinical trials using a pain medication intervention prior to surgery, our sample of 100 will be enough to detect a difference, should one exist. Moreover, the intervention and placebo will be administered randomly with an overall ratio of 1:1 to maximize power for analysis.

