### 9.3 POPULATIONS FOR ANALYSES

Intention to treat analysis will be used for the study. Other sensitivity analyses will include analyses for treatment as administered.

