### 9.4 STATISTICAL ANALYSES

#### 9.4.1 GENERAL APPROACH

For descriptive analyses categorical variables will be described using the frequency and proportions. Continuous variables will be described using median and the interquartile range (Q1, Q3). All p-values of statistical tests will be two-tailed with a  $p < 0.05$  considered statistically significant.

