#### 9.4.2 ANALYSIS OF THE PRIMARY ENDPOINT(S)

The primary endpoint of differences on pain score will be analyzed using the Wilcoxon rank sum test or Mann-Whitney U test.

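### Day 1-4 pain scores and analgesic use exist only on a paper log returned at two weeks; lost logs cost power, and the call already foreseen could capture the data.

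*Combined protocol and SAP*

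**What the plan says.** **Collection.** Under 4.1 the patient goes home with a worksheet for pain scores and analgesic use on postoperative days 1 to 4, and "They are expected to bring the completed log to their two-week follow up visit". Section 6.4 has the form tracked at the post-operation visit, and 10.1.9.1 makes hard-copy worksheets the source documents. The documents describe no mail, electronic or telephone capture.

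**Contact with patients.** Section 4.1 adds: "Patients may also expect to receive a phone call from a member of the surgical team to remind them to record these metrics". The call is thus possible but not required, and its only stated purpose is to remind. Section 7.3 promises attempts to reach a patient before declaring loss to follow-up, but does not say that scores are collected then.

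**Completion and analysis.** Section 4.4 defines end of study as "completing the intervention and any portion of worksheet". Section 9.3 says "Intention to treat analysis will be used for the study". The primary endpoint "will be analyzed using the Wilcoxon rank sum test or Mann-Whitney U test" (9.4.2). Section 9 names no method for missing scores and makes no allowance for loss. Section 2.2 promises mixed effects models over time for pain scores and opiate consumption, but 9.4 does not take them up.

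**The concern.** The last entry is made on day 4 and the sheet is handed over at about day 14, so the patient must keep it for some ten days and remember to bring it. If it is mislaid or the visit is missed, that patient's postoperative scores and analgesic record are both gone. A rank-sum test can use only the scores that arrive, so the analysis set becomes patients who returned a log, whatever 9.3 says.

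Two things are at stake. The first is power, since every lost log reduces a sample of 100 that has no margin for loss. The second is possible distortion, because return may be related to pain, which is itself the outcome. How much distortion follows depends on whether that relation differs between the arms.

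**Working it through.** **Inputs from the documents.** N = 100 and 1:1 allocation (9.2: "our sample of 100 will be enough to detect a difference, should one exist", with treatment "administered randomly with an overall ratio of 1:1 to maximize power for analysis"), so 50 per arm. Section 9.4.1 says "All p-values of statistical tests will be two-tailed with a" threshold of 0.05. The primary test is the rank-sum test (9.4.2).

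**Not in the documents.** Effect size, SD, target power and expected return rate. The sample size of 100 therefore cannot be reproduced, and what follows is illustrative.

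**Step 1: the effect that 100 patients can detect.** For normal scores the rank-sum test has relative efficiency 3/π, so the effective n per arm is 50 × 3/π = 47.75. At 80% power:

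d = (1.960 + 0.842) × √(2/47.75) = 2.802 × 0.2047 = 0.573 SD.

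This value is assumed as the true difference below.

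**Step 2: logs lost at random.** With a fraction L lost, n = 47.75 × (1 − L) and power = Φ(0.573 × √(n/2) − 1.960). For L = 0.20: n = 38.2, 0.573 × 4.370 = 2.506, and Φ(0.546) = 0.707. Simulation of the Mann-Whitney test (50 per arm, several thousand replicates) gives slightly lower values; repeat runs differ by about a point.

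| Logs lost | Power, formula | Power, simulated |
|---|---|---|
| 0% | 80.0% | 78-79% |
| 5% | 78.0% | 77% |
| 10% | 75.7% | 75% |
| 20% | 70.7% | 69% |
| 30% | 65.0% | 62% |

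At 20% loss the difference detectable with 80% power grows from 0.57 to 0.64 SD. Random loss leaves the estimate unbiased.

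**Step 3: loss related to pain, same rule in both arms.** Return follows a logistic model with slope 1 per SD of pain and 73% return at the placebo mean.

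| Who returns less | Overall loss | Raw difference | Standardised difference | Power | Type I error |
|---|---|---|---|---|---|
| Higher pain | 26% | 0.50 SD | 0.54 | 60% | 4.8% |
| Lower pain | 36% | 0.49 SD | 0.53 | 52% | 5.1% |

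The raw difference shrinks more than the standardised one because selection also narrows the spread. Most of the power loss is ordinary sample loss. With 80% return at the placebo mean, the same model loses 20% or 29% of logs and gives 64% or 57% power, against about 69% and 63% for random loss of that size. Dependence on pain thus adds about 5 to 6 points.

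**Step 4: loss related to pain in opposite ways by arm.** Suppose that in one arm 30% of logs are lost above the placebo mean and 10% below it, and in the other arm the reverse. Overall loss is about 20%. The estimate moves from 0.57 to 0.38 or 0.75 SD, depending on which arm is which. With no true effect, type I error is about 16%. In these scenarios, this is the only pattern that produces false positives.

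**The case against.** **The figures are assumed.** This stands. The 0.57 SD is back-solved from N = 100, and the loss rates and return models are chosen. At 5% or 10% loss the cost in power is only a few points. A reader might infer that 20-30% loss is to be expected; nothing in the documents supports any particular rate.

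**Contact is already promised.** Section 7.3 does give a route to patients who miss the visit. It stands as a partial safeguard. However, it specifies no data capture and does not clearly cover a patient who attends without the log.

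**The stronger reading on bias fails.** A reader might infer that pain-related loss by itself makes the result misleading. Step 3 shows otherwise: the same dependence in both arms attenuates the difference and leaves type I error near 5%. The documents give no evidence of loss that differs by arm.

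**Section 4.4 is not the fault.** A reader might take the acceptance of partial worksheets as what undermines intention to treat. It does the opposite, since it keeps data that a longitudinal model can use. The complete-case problem comes from unreturned logs combined with a test that has no provision for them.

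**Not every outcome is exposed.** Complications, the exploratory endpoint, are not tied to the log. The endpoint in section 3 is also a change in score, and the documents do not say where a baseline comes from. The point therefore covers postoperative scores and analgesic use only.

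**Telephone capture has weaknesses.** A call on any convenient day would yield different days for different patients, and scores recalled at two weeks are poor data. Both objections stand and shape the fix.

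**Conclusion.** The concern holds in limited form. Postoperative pain scores and analgesic use have a single route into the database, a paper log returned at two weeks, and neither the call in 4.1 nor the contact in 7.3 backs it up. Logs that are not returned turn the primary test into a complete-case analysis.

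Under an assumed 0.57 SD difference, the certain cost is power: from just under 80% with all logs to about 69% with 20% lost at random. Attenuation to about 0.49-0.50 SD raw (0.53-0.54 standardised) is possible if return depends on pain alike in both arms. Material bias and inflated type I error arise only if that dependence differs by arm, which is conceivable but not shown. The trial is not invalidated. The change is worth making because the weakness is avoidable at small cost.

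**What to change.** 1. **Section 4.1:** make the foreseen call to every patient, on one fixed postoperative day within days 1-4. The caller records that day's pain score and analgesic intake, and any earlier log entries that the patient reads out. The caller should be an existing team member unaware of allocation. This needs stating because 4.1 has the call made by the surgical team and also has the envelope inform the anesthesiologist or surgeon.
2. **Section 7.3:** use the contact to obtain entries already written on an unreturned log. Flag anything given from memory and examine it in a sensitivity analysis.
3. **Section 9.4.2:** carry over the mixed model promised in 2.2, so that all available days, including partial logs, are analysed. State which contrast is primary. The model cannot recover a patient with no recorded day and does not remove arm-specific loss, so it complements the call and does not replace it.
4. **Reporting:** give log-return rates by arm, so that differential loss is visible.

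**Cost.** Calls become routine for all 100 patients within a four-day window, which is more work than occasional reminders. Telephone and paper entries are mixed, so the source of each must be recorded.

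**Gain.** If, for illustration, capture cut loss from 20% to 5%, power would rise from about 71% to 78% by the formula. Keeping 100 evaluable patients by over-recruitment alone would need 100/0.8 = 125 randomised at 20% loss.
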